The Director, CSP, can terminate a cooperative study before completion. The DMC makes recommendations as to whether the study should continue or be terminated. The decision to terminate a study prematurely is a complex one involving many factors. The DMC may consider the following circumstances as grounds for early termination:

1. If patient accrual falls far below that which is predicted (e.g., 75% of expected accrual), it will be necessary to reassess the study design and the potential value of its continuation.
2. If patient accrual far exceeds the predicted, this study could be completed at an earlier date.
3. If serious adverse events or mortality are noted to be excessive in either treatment group.

Termination by recommendation of the DMC will be carried out as outlined in CSP Guidelines.

Quality Control through the Boston CSPCC Quality Management System

The quality management system (QMS) in place at the CSPCC will ensure further quality control for CSP 594. The Quality Assurance Department of the CSPCC will subject the data to risk based audits and monitoring that will verify and validate data elements according to internal SOPs. In brief, a sample of the data will be verified at routine intervals. If errors are identified they will be referred to the data management team for resolution. If the error level rises to a predefined threshold, then the entire record or data element type will be subjected to verification and validation. Further, the CSPCC will conduct internal audits to ensure the quality of the clinical trial processes and procedures. If deviations or non-conformances are identified they will be remedied through the internal corrective action/preventive action system of the QMS.

Risk based monitoring and auditing will also allow for the early systematic identification of problems that require remediation at the clinical site level. If problems are identified, the CSPCC will work with the clinical site to create a remediation plan to address the issues. If the problems persist after remediation, the site may be recommended for closure to the executive committee.

XIX. Good Clinical Practice (GCP)

Role of GCP

This trial will be conducted in compliance with Good Clinical Practices (GCP) regulations. The intent of these regulations is to safeguard participants' welfare and assure the validity of data resulting from the clinical research. The VA Cooperative Studies Program will assist LSIs in complying with GCP requirements through its Site Monitoring, Auditing and Resource Team (SMART) based in Albuquerque, NM. SMART serves as the Quality Assurance arm of CSP for GCP compliance. Study site personnel will receive a GCP orientation at the study kickoff meeting. SMART will provide training, manuals, and materials to assist study personnel in organizing study files and will be available throughout the trial to advise and assist LSIs regarding GCP issues.

Summary of Monitoring and Auditing Plans:

Monitoring Visits

- Initial visits at each site soon after study start-up
- Subsequent monitoring will be conducted yearly.
- Final monitoring visit to each site during last year of the study
- Additional monitoring visits may be conducted as deemed necessary by study leadership or SMART.

Audits

- Routine audits –independent site visits to one or more sites per year as determined by SMART
- For-Cause audits – independent audits of a site as requested by study leadership or CSP Central Office.

Note: Audits may be scheduled or unannounced

XX. Study Organization and Administration

A. Administration

The administrative structure of this study is similar to others in CSP and includes:

The Cooperative Studies Program (VA Central Office) establishes overall policies and procedures that are applied to all VA cooperative studies through the Study Chair's office and the CSPCC.

The CSPCC and the **Study Chair's office** jointly will perform the day-to-day scientific and administrative coordination of the study. These include developing and revising the study protocol, Operations Manual, and case report forms; ensuring the appropriate support for the participating centers; scheduling meetings and conference calls; answering questions about the protocol; conducting site visits; publishing newsletters; preparing interim and final progress reports; and archiving study data at the end of the study. Study progress reports will be produced every 6 months. Patient accrual, patient safety, and data quality will be monitored closely to ensure that the study is progressing satisfactorily.

The CSP Clinical Research Pharmacy Coordinating Center (CSPCRPCC) manages the pharmaceutical aspects of multicenter pharmaceutical and device clinical trials including patient safety monitoring. CSPCRPCC acts as a liaison between the study participants, the FDA, and the manufacturers of the study drug(s) or device(s) in all VA Cooperative Studies that involve drugs or devices. The CSPCRPCC develops Drug Treatment and Handling Procedures, obtains and distributes the study drug(s), prepares a Drug Information Report for the study drug, and provides advice and consultation about drug-related matters during the study. CSPCRPCC is responsible for monitoring and reporting the safety of trial participants through the review, assessment, and communication of adverse events and serious adverse events reported by study personnel with reviewing responsibilities occurring through ongoing communication with the Study Chair, Executive Committee, CSPCC, and CSP Central Office. The reporting activities include filing regulatory documents involving adverse events with the FDA and manufacturers to meet federal regulations and CSP policies. In conjunction with the CSPCC, the CSPCRPCC trends and analyzes safety data to prepare reports for various committees including the DMC, VA Central IRB (CIRB), Executive Committee(s), and Study Group meetings.

Each **participating VA medical center** will designate a site investigator (SI) to be responsible administratively and scientifically for the conduct of the study at the center. SIs will be expected to attend all annual Study Group meetings, as well as to hire and supervise personnel. By agreeing to participate in the study, the medical center delegates responsibility for global monitoring of the ongoing study to the DMC, the CSPCC Human Rights Committee, and the CSSEC.

The Clinical Sciences Scientific Evaluation Committee (CSSEC) reviews the scientific merit of all new cooperative study proposals and all ongoing cooperative studies every 3 years. The committee is composed of both VA and non-VA clinical research scientists, most of whom have had experience in managing their own cooperative studies.

The Study Group will be composed of the SIs from each participating center, the Study Chair, Study Director, and CSP staff (biostatistician, project manager, clinical research pharmacist, and others).

The Study Chair will head the group, which will meet once a year to discuss the progress of the study, any problems that the investigators have encountered, and any suggestions for improving the study.

B. Monitoring

The following groups monitor the various aspects of the study. These committees will meet according to current Cooperative Studies Program guidelines. In addition, the CSP SMART will monitor the trial for GCP compliance as indicated above.

The Executive Committee is responsible for the operations of the study, including protocol amendments, and overall management of the study. It will be headed by the Study Chair and Study Director and consist of the study biostatistician, study project manager, clinical research pharmacist, selected participating investigators, and outside consultants as needed. This committee will meet regularly to review blinded data (not broken down by treatment group), decide upon changes in the study, determine the fate of hospitals whose performance is substandard, initiate any sub protocols, and discuss publication of the study results. This Committee must grant permission before any study data may be used for presentation or publication.

The Data Monitoring Committee (DMC) will review the progress of the study and will monitor patient intake, outcomes, adverse events, and other issues related to patient safety. Interim, independent, and unbiased reviews of the study's ongoing progress will be provided. The DMC will consist of experts in the study's subject matter field(s), clinical trials, biostatistics, and ethics. These individuals will not be participants in the trial and will not have participated in the planning of the protocol. The DMC will consider safety or other circumstances as grounds for early termination, including either compelling internal or external evidence of treatment differences or the unfeasibility of addressing the study hypothesis (e.g., poor patient intake, poor adherence to the protocol).

At each of its meetings during the study period, the DMC will review the randomization rates and assess the difference between the actual and the projected rates, as well as the impact of these assessments on overall trial size. If the study enrollment is inadequate, the reasons for exclusion may be scrutinized and actions may be suggested. An assessment of whether the trial should be continued will be made followed by recommendations, as appropriate. All serious adverse events will be reported regularly to the DMC for review. Unexpected, related serious adverse events will be reported to the DMC as soon as they become known based upon the consensus of the Study Chair, the study biostatistician, the Study Director, and the study pharmacist. The study biostatistician will provide the appropriate data to the DMC at specified intervals for this purpose. Conditional power estimates will be provided to the DMC to assist them in making their decisions and recommendations. To help them make their assessment, the Study Chair and study biostatistician will furnish the Data Monitoring Committee with appropriate monitoring data before each meeting. The DMC makes recommendations after each meeting to the CSP Director about whether the study should continue or be stopped.

The VA Central IRB will be the IRB of record for all VA sites. They will monitor the study's serious adverse events and review deviations on a continual basis. They will conduct annual reviews of the study. All local sites may be required to submit reports to their local Research and Development and/or Safety Committee for approval. In addition, some study materials (such as participant correspondence and protocol changes) will have to be reviewed by the VA CIRB, and approved prior to implementation.

The **CSPCC Human Rights Committee (HRC)** is composed primarily of lay people and is responsible for ensuring that patients' rights and safety are upheld prior to study initiation and during the conduct of the study. The committee reviews all new protocols, periodically makes site visits to participating centers to monitor firsthand the progress of the study, and may be asked to review any ethical and human rights issues that arise during the conduct of the study.

The CSP Site Monitoring, Auditing and Resource Team (SMART), located at the CSPCRPCC in Albuquerque, will monitor the trial for compliance with Good Clinical Practices (GCP). GCP monitors from SMART will visit participating sites shortly after enrollment is initiated and subsequent monitoring will be conducted yearly thereafter to ensure investigator regulatory and protocol compliance and to evaluate research practices. SMART will provide an orientation to GCP at the study kick-off meeting and provide GCP tools to enhance compliance. Additionally, SMART will conduct periodic routine audits throughout the course of the study and for-cause audits as requested by study leadership or CSP VACO.

XXI. Publications

Publication policy

It is the policy of the CSP that outcome data will not be revealed to the participating investigators until the data collection phase of the study is completed. This policy safeguards against possible biases affecting the data collection. All presentations and publications from this study will be done in accordance with current CSP Guidelines, including the Authorship Policy. The most current version of the Guidelines should be referenced when planning any study publication. The presentation or publication of any or all data collected by participating investigators on patients entered into the VA Cooperative Study is under the direct control of the study's Executive Committee. No individual participating investigator has any inherent right to perform analyses or interpretations or to make public presentations or seek publication of any or all of the data other than under the auspices and approval of the Executive Committee.

The Executive Committee has the authority to establish one or more publication subgroups of investigators and members of the Executive Committee for producing scientific presentations and publications. Authors with VA appointments must list their VA affiliation first. The VA contributions to the research project should be acknowledged in all written and oral presentations of the research results, including scientific articles, news releases, news conferences, public lectures, and media interviews.

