***COVID-19:**

Due to COVID-19, in-person visits may be conducted via telephone if an in-person visit is not feasible. Safety for all subjects, health care staff and others should be considered prior to every study visit. The Local Site Investigator has the discretion to determine what type of visit (in-person or telephone) is most appropriate. Sites are to adhere to the strictest safety policies and procedures in place. If local policies and procedures allow for in-person research visits to occur, this is the preferred method of sample and data collection. However, if an in-person visit is not feasible and a telephone visit is conducted instead this would not be considered a protocol deviation. Sites are to collect the protocol specified lab values for weeks 48, 60 and 72 even if the visit is conducted via telephone. Sites are permitted to utilize a CBOC for lab draws. If subjects are unable to have labs drawn due to COVID-19, lab values within the CPRS system that are drawn during the visit window can be used to supplement the study specified labs at a given visit. If no lab values are obtained for weeks 48, 60 and 72, this will be considered a protocol deviation.

Proposed Design:

Participants will be recruited from 20 Veteran Affairs and 5 RAIN sites. Individuals with a history of gout who continue to be hyperuricemic (sUA \geq 6.8mg/dl) and fulfill entry criteria will be invited to participate. In this prospective double-blind non-inferiority trial, 950 participants will be randomized in a 1:1 ratio to receive either allopurinol or febuxostat. Recruitment will occur over 24 months. The total duration of the trial will be 4 years.

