The primary outcome will be the proportion of participants who have at least one gout flare in the Allopurinol group compared with the febuxostat group during Phase 3. Flare ascertainment during Phase 3 has been deliberately chosen (rather than during Phase 1 or 2) with the understanding that gout flares are a commonly experienced physiologic consequence of ULT during the first year of therapy, and usually indicate successful urate lowering rather than treatment failure. All participants will be followed during Phase 3 regardless of the achievement of sUA goal. The primary hypothesis will test the non-inferiority of allopurinol based upon the proportion experiencing ≥ 1 flare in each of the two treatment groups in Phase 3.

Randomization:

Balanced randomization will be used to ensure that equal proportions of participants with the following characteristics are in the two treatment arms: 1) CKD Stage 3 (individuals with CKD Stages 4 and 5 will be excluded); 2) marked hyperuricemia defined as a sUA ≥ 9.0 mg/dl; 3) presence of tophi (focused examination involving the hands, elbows, feet, and ears, which are the most common sites for tophaceous deposits); and 4) participants with prior receipt of ULT. All of these factors have been associated with a lower likelihood of achieving sUA goals in recent head-to-head trials of these two agents (12, 13). Further, to guarantee enrollment of a sufficient number of gout participants with CKD stage 3 (eGFR ≥ 30 but < 60 ml/min) to address a key secondary objective (see above), we will randomize at least one participant with CKD Stage 3 for every two participants with preserved renal function (eGFR ≥ 60 ml/min).

VII. Outcome Measures

Primary Outcome:

The primary outcome will be the proportion of participants who have at least one gout flare in the Allopurinol group compared with the febuxostat group during Phase 3.

Gout flares:

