Both the five-item EurQol (EQ-5D-3L) and Veterans RAND 12 (VR-12) will be collected from all participants at baseline, 24, and 48 weeks. The EQ-5D-3L is a widely used measure of generic health-related quality of life, which is relatively brief and provides a single index utility value (78). This measure has been shown to be valid and reliable in assessing health-related quality of life in a number of chronic health conditions and will enable future cost-effectiveness analysis. Results from the EQ-5D-3L will be supplemented with those from the VR-12, an alternative measure of health-related quality of life. Similar to the EQ-5D-3L, the VR-12 survey is relatively brief and demonstrates excellent validity and reliability. Of special note, the VR-12 allows for computation of both Physical and Mental Health Scale scores. Although gout-specific health-related quality of life measures have been proposed, these measures have not been consistently demonstrated to have sufficient levels of validity or reliability (79).

- 5) Changes in tophi area by location among those with tophaceous gout across treatment groups and sUA levels.

Based on data from a recent clinical trial in chronic gout, we anticipate that ~20% of study participants will have tophi at enrollment (12). Change in tophi area (see below for assessment procedure) will be examined as a secondary outcome among this informative subset of patients with tophaceous gout. Providing rationale for their consideration as a secondary outcome, tophi are pathognomonic of gout and are problematic for patients as they mediate joint damage, often result in troubling cosmetic issues, and frequently obstruct normal joint function.

For this study, a sentinel tophus will be measured at enrollment and the same tophus will then be measured in follow-up at weeks 24 and 48 using tape measurement as recently detailed by Dalbeth et al. (80). The sentinel tophus will be defined as the most prominent and/or most readily measured

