tophus found at the time of the baseline evaluation on the hands, elbows, feet, or ears (i.e., the most common sites for tophi). In addition to having face validity, the tape measurement technique is inexpensive, requires minimal training, and a very short time for acquisition (estimated to be < 5 minutes). Moreover, this technique yields excellent inter- and intra-observer reliability with interclass correlation coefficients exceeding 0.9. In a 52-week study, patients with tophaceous gout achieving a final serum urate < 6.0 mg/dl demonstrated a 75% reduction in tophus size using this technique (11).

6) The impact of treatment on the flare rate over time (comparison of flare rates during each phase).

To determine whether the total number of gout flares differs between the two treatment groups the total flare numbers occurring during observation (week 0 to 72) will be compared. Recognizing that the duration of a gout flare typically extends from several days to 2-3 weeks, and that it may sometimes be difficult for patients to distinguish between two or more back-to-back flares and one persistent but fluctuating flare, a maximum of one gout flare will be counted for each one-month observation period. Thus, as an example during Phase 3 (24 weeks) patients could experience a number of gout flares ranging from 0 to 6 flares.

7) Exploring the tolerability/toxicity of the two ULT.

Toxicity data will be carefully collected throughout the 72 weeks of the trial (See Section XI, Baseline and Follow-up Assessment) and compared across treatment arms. Adverse events will be summarized using Medical Dictionary for Regulatory Activities (MedDRA) terminology and reported by count and frequency (%) for participants reporting an event for each term. Toxicity data that will be systematically collected include rises in sUA levels, serum creatinine, CBC, liver function tests (LFTs), blood pressure and reports of skin rashes. The frequency of cardiovascular safety events of interest will also be collected and analyzed, with particular emphasis on cardiovascular and all-cause mortality. Investigators will report other treatment-related adverse events should they encounter them. All hospitalizations and other adverse events defined as serious per ICH guidelines will be collected and analyzed by treatment group.

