The test of the primary hypothesis compares the treatments without adjustment for any covariates. The secondary analyses, particularly secondary analysis will confirm or not confirm the primary hypothesis by considering variations on the primary analysis including logistic regression models that adjust for covariates. We note that logistic regression analysis yields a treatment odds ratio rather than the difference between proportions. In this case, to carry out the non-inferiority test, we will estimate the difference between treatments by linking the odds ratio to the overall proportion of participants who have one or more gout flares.

In addition to testing the primary hypothesis, extensive descriptive analyses outlined in (BRDP) will compare treatments with respect to selected variables among the demographic, medical history, laboratory values, anthropomorphic, vital sign, quality-of-life, alternative outcome, and side effect variables. Simple unadjusted comparisons will apply Student's t-test to continuous variables, the Wilcoxon test to highly skewed continuous or ordinal variables and will apply the Chi-square test (or Fisher's exact test) to categorical variables.

Non-adherence

Of relevance to this study, observational studies have indicated relatively poor adherence in patients with gout (40, 87-90) However, Dalbeth et al. (91) found that higher doses of allopurinol were associated with sUA levels at target independent of adherence with treatment. Because all study participants will receive active therapies of proven efficacy for lowering sUA levels as well as prophylactic treatment of acute gout symptoms, compliance issues are expected to be minimal in this trial. Other studies in rheumatoid arthritis have shown that if patients are doing well, issues of poor treatment adherence are minimized (92).

Participant adherence to protocol-directed study treatment will be assessed via pill counts, prescription renewals, and participant interview. We will use the question and pill count data to determine if a participant took 80% or more of treatment medication. The per-protocol population will be defined as participants remaining on the same treatment throughout the entirety of the study with 80% adherence.

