Tophi area will be assessed at baseline, 24 and 48 weeks. At each time point we will compare the mean areas by location by treatment groups, using an unadjusted t-test and linear regression with adjustment for baseline covariates. Also, with area change from baseline to 24 weeks and area change from baseline to 48 weeks, we will compare mean changes by location with and without covariates using linear regression. Finally, we will carry out a repeated measures analysis using all three times. Missing data methods will address potential censoring of events among patients who fail to complete the instrument at a particular time. Analogous analyses will be carried out controlling for sUA levels.

- 6) To determine whether the number of gout flares during all three phases differ between participants randomized to allopurinol compared to febuxostat and then extend this analysis to the entire 72-week period.

We will model the number of gout flares, which can have substantial variation, as Poisson random variables. The analyses will compare treatments using a longitudinal repeated measures analysis with Poisson counts (PROC GLIMMAX and GENMOD in SAS). Missing data methods will address potential censoring of events among patients who appear to fail to report flares. Flare counts will be analyzed separately during Phases 1, 2, and 3 because dose titration during Phase 1 tends to increase the counts, and this effect may still persist in Phase 2, particularly for those still undergoing dose titration; participants are expected to be in steady-state by Phase 3. Also, Phase 2 analysis will consider prophylactic treatment after a gout flare and severe side effects of treatment as predictors of subsequent counts. During Phase 3 the same set of factors as well as Phase 2 counts will be used to predict gout flare counts. These time-dependent associations will require a mixed effects model using an auto correlated variance-covariance to model the series of events. For these analyses we may treat

the counts as continuous measures in order to introduce more subtle variance-covariance structure and a variety of random effects.

- 7) To determine the patterns of tolerability/toxicity for each treatment during Phase 3 and then overall from weeks 1-72.

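### Objective 5 compares tophus area by location although each participant has one measured tophus, and it names no pooled drug comparison as the main analysis

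*Protocol*

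**What the plan says.** Protocol VII (secondary outcome 5) follows one lesion per person: "a sentinel tophus will be measured at enrollment and the same tophus will then be measured in follow-up at weeks 24 and 48". The sentinel lesion is the most prominent or most easily measured "tophus found at the time of the baseline evaluation on the hands, elbows, feet, or ears". Table 5 records tophus location at baseline only, and SAP Table A7 lists a single index-tophus form.

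The analysis of objective 5 (Protocol VIII; SAP 5.5) has three parts:

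- **Levels:** "At each time point we will compare the mean areas by location by treatment groups, using an unadjusted t-test", together with linear regression adjusted for baseline covariates.
- **Changes from baseline:** "we will compare mean changes by location with and without covariates using linear regression".
- **Repeated measures over all time points:** location is not mentioned, and no model is given.

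The objective is itself framed by location (Protocol V; SAP 2). Both documents call all secondary analyses descriptive and exploratory. Neither gives an SD, a target difference, a power figure, a split by site or a multiplicity rule for tophus area.

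**The concern.** Location is a fixed attribute of the participant here, not a repeated factor within the participant. A by-location comparison therefore spreads an already small subgroup over several cells and gains no data in return. The wording looks deliberate: the parallel paragraph for quality of life (objective 4) has almost the same structure without any such split.

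At stake is the precision of the drug comparison on tophi. Read as written, the plan yields several imprecise site-level contrasts. The one estimate that could use everyone with tophi depends on a repeated-measures sentence that leaves the role of location open. Separate tests at each site also do not test whether the drug effect differs between sites, which is what a by-location question asks.

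**Working it through.** The documents state no power or sample size for tophus area, so there is no figure to reproduce.

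**Inputs from the documents**

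- Total and allocation: "950 participants will be randomized in a 1:1 ratio to receive either allopurinol or febuxostat" (Protocol VI).
- Share with tophi: "we anticipate that ~20% of study participants will have tophi at enrollment" (Protocol VII). Presence of tophi is a balancing factor at randomization, which supports near-equal numbers per arm.
- Four sites: hands, elbows, feet, ears.

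**Assumptions, not in the documents:** two-sided 5%, equal spread over sites, no dropout, and a 0.5 SD difference for illustration.

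**Numbers per cell**

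- With tophi: 0.20 × 950 = 190, so 190 / 2 = 95 per arm.
- Per arm per site: 95 / 4 = 23.75, about 24.

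**Detectable difference at 80% power.** The normal approximation is (1.960 + 0.842) × √(2/n):

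- Pooled, n = 95: 2.802 × √(2/95) = 0.41 SD.
- Per site, n = 23.75: 2.802 × √(2/23.75) = 0.81 SD.

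The exact t-test gives 0.409 and 0.831 SD. A quarter of the sample roughly doubles the detectable difference.

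**Power at 0.5 SD** (two-sample t-test, noncentrality 0.5 × √(n/2)), with the assumptions varied:

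| Case | n per arm | Detectable at 80% power | Power at 0.5 SD |
|---|---|---|---|
| Pooled | 95 | 0.41 SD | 93% |
| Pooled, 5–15% attrition | 90–81 | 0.42–0.44 SD | 92–89% |
| One site, equal split | about 24 | 0.83 SD | about 40% |
| One site, 5–15% attrition | 23–20 | 0.85–0.91 SD | 38–34% |
| Site with 10% of tophi | 9.5 | 1.36 SD | 18% |
| Site with 50% of tophi | 47.5 | 0.58 SD | 67% |

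The attrition range spans the documents' own figures: 5% in the protocol's power section, 10% in SAP 4 and up to 15% under Missing Data in the protocol. If 15% or 25% of participants have tophi, the pooled figure becomes 0.47 or 0.37 SD and the equal-split site figure 0.97 or 0.74 SD.

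**Multiplicity at one time point.** The four sites hold different people, so their tests are independent: 1 − 0.95⁴ = 0.185, about 19%.

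**Schedule.** Protocol VII, VIII and Table 5 measure tophus area at baseline, 24 and 48 weeks. SAP 3.5.2 and 5.5 add week 72.

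**The case against.** A reader might infer that the drug comparison on tophi cannot be answered. The documents do not support that. The repeated-measures sentence carries no location split, so it may pool sites, and about 95 per arm pooled is reasonably informative. Nor are t-tests the only method: adjusted regression is planned too, and there by location could mean a factor or an interaction. An unadjusted t-test, however, has no place for a location term, so for that comparison separate site tests are the natural reading.

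A reader might also multiply four sites by two follow-up times and quote 1 − 0.95⁸ = 34% for a false positive. That treats weeks 24 and 48 as independent, although the same tophus is measured at both. The 19% figure at one time point is the defensible one.

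It would also go too far to say that a real difference would usually be missed. No SD or expected difference is given, and a site holding half of the tophi would have 67% power at 0.5 SD.

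Two objections stand in part. The analyses are declared exploratory, which limits how much this matters, but it is no reason to prefer the less precise estimate from the same data. The objective does ask about location, and a treatment-by-location term answers that more directly than separate tests.

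On skewness, the protocol gives no data. It cites a 75% reduction in tophus size in an earlier study and foresees resolution of tophi, so areas near zero are plausible. Its general text assigns "the Wilcoxon test to highly skewed continuous or ordinal variables", but objective 5 does not take this up.

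**Conclusion.** The point holds as a weakness of efficiency and clarity in one exploratory secondary objective. Followed as written, the level and change comparisons use cells averaging about 24 per arm where about 95 are available. The detectable difference roughly doubles, from 0.41 to 0.83 SD. At an assumed 0.5 SD, power falls from 93% to about 40%, with a range of 18% to 67% for sites holding 10% to 50% of tophi.

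These figures rest on the documents' 20% expectation, a two-sided 5% level and no dropout; the headline per-site figures also assume an even split. A loss of precision at each site remains under every split and attrition rate examined. Whether a pooled estimate will be produced cannot be settled from the text, because the repeated-measures sentence does not specify it. The primary analysis is not affected.

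**What to change.** In SAP 5.5, objective 5, and the matching text of Protocol VIII:

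1. Name one lead analysis: the difference between arms in change in sentinel tophus area over all participants with baseline tophi, adjusted for baseline area and with location as a factor. State the time point it leads on; week 48 is the latest that both documents contain.
2. Apply the same specification to the repeated-measures model, so that the role of location is explicit.
3. Test a treatment-by-location interaction and give site-specific estimates with confidence intervals as description. The interaction test will itself be imprecise and should be read that way.
4. Name a site-stratified rank test as the alternative if areas are highly skewed or often zero, consistent with the protocol's own rule on skewed variables. Make that choice on data pooled over arms, before unblinding.
5. Reconcile the SAP's week-72 tophus assessment with the protocol's schedule.

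Items 1 to 4 need wording only and use data already being collected. The price is that by-location results become descriptive, and the protocol text needs a wording amendment with the usual approval.
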